3.2 Secondary

Objective	Brief Description/Justification of Outcome Measure	Outcome Measured By	Time Frame
Assess image quality and subject pain	Comparison of image quality between the SOC scope and FNS as well as subject perception of pain between the two exams will help to inform modifications needed for prototype optimization.	image quality of each scope: rated 1(poor) to 5 (excellent) perceived pain by subjects between scopes: Much More 1 About the same 2 Much Less 3	up to 2 months

4 STUDY DESIGN

The Optimization Phase (Phase 1) Due to new regulatory restrictions in Vietnam, the optimization phase for Aim 1 will now be conducted at Duke University. This will allow us to obtain data from subjects and providers that will be helpful in determining if additional adjustments or improvements are needed to the FNS prototype. Direct comparison between the current approach using available SOC flexible scopes with the new approach using the low cost FNS will be made. Potential eligible subjects being seen in the Duke Head and Neck Surgery and Communication Sciences clinic meeting clinical indication for a SOC scope exam will be approached for the study. If consent is given, the subject will first undergo the “SOC” scope endoscopy. Then the FNS exam will be performed using the prototype. A post-procedure survey will then be administered and completed by both the provider and subject. Post-procedure data will be collected in three areas: technical assessment, physician feedback, and subject feedback.

The entire study procedure after consent takes about 5 minutes: ~one minute for the SOC scope procedure, ~one minute to change to the FNS scope, ~one minute for the FNS procedure, ~one minute to complete the study survey. We will have at least two low cost FNS to use. To allow for high level disinfection (HLD) between use, we will recruit 2 study participants in the morning clinic session, and 2 in the afternoon for a total of 4 participants per day.

Data will be collected using REDCap on a tablet to enable real time data collection. REDCap is a browser-based survey data collection platform. The data input tablet will be password protected and coded. Data will be stored in the REDCap database. Data will be collected after each FNS scope procedure and will include a technical assessment from the physician. This assessment includes ease of use, and quality of the image. Finally, the subjects will use a numeric scale to assess and compare pain experience between the two scope procedures. Collection of adverse events will also be via REDCap at this time.

The study participation is completed on the scope when survey information is collected. Data collection for each FNS prototype will involve a cohort of up to 50 subjects.

This technical and subjective feedback from subjects and providers will be used to optimize the device during the Optimization Phase. Each outcome measure as described in Section 3.1 and 3.2 will be compared between the SOC scope to the low cost FNS and used as a basis for modifications. For example, if the low-cost FNS image quality is noted to have lower ratings compared to the SOC scope due to inadequate lighting, modifications will be made to increase the light output for the next prototype.

The goal is to modify the prototype so that the outcome measures from the low cost FNS meet or exceed the outcome measures from the SOC scope. If this is the case, no

further prototypes will need to be performed for the optimization phase. Thus, the threshold for success will be noninferiority of the FNS compared to the SOC scope.

In addition to survey feedback, the FNS will have capacity to capture anonymized images of the upper aerodigestive tract such as the oropharynx, larynx, and nasopharynx. These will be collected and stored to a centralized image library. There will be no link to the subject, thus preventing loss of confidentiality.

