3 OBJECTIVES AND OUTCOME MEASURES

OBJECTIVES:

We will collect user feedback and reliability of the low-cost FNS scope as compared with the currently used SOC scope procedure. Collection of technical issues with the low cost FNS prototypes will also include steering, lighting, video, fogging, image capture.

Key objectives include comparisons between the SOC scope and FNS:

Primary

Ease of use

Compared with the first scope, how easy was the second scope to use?

Very Hard	Harder	same	Easier	Very Easy
1	2	3	4	5

Secondary

1) Image Quality

Rate the video quality of the first scope: (Poor) 1 2 3 4 5 (Excellent)

Rate the video quality of the second scope: (Poor) 1 2 3 4 5 (Excellent)

2) Perceived pain by subjects

Did you experience more, the same, or less pain/discomfort with the second scope compared with the first scope?

much more about the same much less

1	2	3
---	---	---

OUTCOME MEASURES

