7 STUDY SCHEDULE

7.1 Enrollment/Baseline

- Obtain and document consent from participant on study consent form.
- Verify inclusion/exclusion criteria.
- Administer the SOC scope then FNS study intervention.
- Administer post procedural surveys:
 - Provider survey
 - Subject survey

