12 STATISTICAL CONSIDERATIONS

12.1 Study Hypotheses

The study hypothesis is that a low cost FNS can be non-inferior to the SOC scope in terms of ease of use, image quality, and perceived pain.

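### The SOC scope always goes first and the FNS second, so the ease and pain ratings cannot separate device from order and cannot support non-inferiority of the FNS on those two outcomes

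*Combined protocol and SAP*

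**What the plan says.** **Order.** Section 4 has each consented subject undergo the SOC endoscopy first; "Then the FNS exam will be performed using the prototype" follows. Section 7.1 repeats it: "Administer the SOC scope then FNS study intervention". The gap is short: Section 4 allows about "one minute to change to the FNS scope". No randomised or alternating sequence, separate control group or adjustment for order is described.

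**Measurement.** The primary outcome (Sections 3 and 3.1) is one question to the clinician: "Compared with the first scope, how easy was the second scope to use". The pain outcome is one question to the subject: "Did you experience more, the same, or less pain/discomfort with the second scope compared with the first scope". Image quality differs, because each scope gets its own score from 1 to 5.

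**Claim.** Section 12.1: "The study hypothesis is that a low cost FNS can be non-inferior to the SOC scope", on ease, image quality and pain. Section 4: "Thus, the threshold for success will be noninferiority of the FNS compared to the SOC scope". The Précis and Objectives in the Protocol Summary also define success as non-inferiority.

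**Decision rule.** Under Section 12.3 the phase succeeds at 37 subjects if 90% give a same-or-better answer on all three outcomes. Rates from 50% to below 90% lead to recruitment up to 50 and a second assessment. The planned tests are a paired Z-test or Wilcoxon test.

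**Screen.** Under Sections 5.2 and 5.3, subjects who have complications from the SOC exam or cannot tolerate it do not go on to the FNS.

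**The concern.** A second pass can differ from a first whatever instrument is used. The clinician has just seen the same anatomy, which could make the second exam easier. The nose and throat were instrumented about a minute earlier, which could make it more uncomfortable, or less so if the subject has become used to it. Ease and pain are asked only as second against first, so any such effect enters the ratings in full and is read as a property of the FNS.

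The result decides whether prototyping stops or the device is modified again. If going second helps, an inferior prototype could pass. If going second hurts, an adequate one could be sent back. There is also a mismatch with intended use: Section 2.3.2 foresees the FNS where no other scope exists, so it would be the first and only exam there. The trial observes it only as a second pass, in people who have just tolerated a first.

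**Working it through.** **1. The plan's own figure.** Section 12.2 gives n = 37 for a two-sided 95% interval of width 0.2 at a proportion of 0.9, with limits 0.76 and 0.96. The Wilson score interval reproduces this:

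- centre = (p + z²/2n) / (1 + z²/n)
- half-width = z·√[p(1−p)/n + z²/4n²] / (1 + z²/n)
- p = 0.9, n = 37, z = 1.96: centre 0.862, half-width 0.099, limits 0.763 and 0.962, width 0.199
- n = 36: width 0.202, so 37 is the smallest n that meets the target

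This is a precision calculation for one proportion. It contains no order component.

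**2. What the ratings identify.** Write the rating in subject i as Yᵢ = δ + π + eᵢ, where δ is the device effect (FNS against SOC), π the effect of being second rather than first, and eᵢ random error. Every subject has the FNS second, so the mean of Y estimates δ + π. Only that sum is identified. A larger n shrinks the random error but leaves π untouched. A paired Z-test or Wilcoxon test of the same ratings tests the same sum.

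**3. How much it could matter.** The documents give no value for π, so the shifts below are assumptions. At 37 subjects, 0.9 × 37 = 33.3, so 34 are needed. At 50, 0.9 × 50 = 45 are needed. Going on to 50 requires 19 to 33 successes at the first look. For one outcome taken alone:

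P(pass) = P(X₃₇ ≥ 34) + Σ over x = 19 to 33 of P(X₃₇ = x)·P(X₁₃ ≥ 45 − x)

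| Same-or-better rate | Pass at 37 | Pass at 50 after continuing | Total |
|---|---|---|---|
| 0.80 | 0.045 | 0.022 | 0.067 |
| 0.85 | 0.174 | 0.085 | 0.258 |
| 0.90 | 0.486 | 0.165 | 0.651 |
| 0.95 | 0.888 | 0.079 | 0.967 |

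Suppose the rate owing to the device alone is 0.85. An order effect of +5 points moves the pass probability from 0.26 to 0.65, +10 points moves it to 0.97, and −5 points moves it to 0.07. From a device-only rate of 0.90, −5 and −10 points give 0.26 and 0.07.

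**4. The cause is the single order, not the sample size.** At the first look only, with a device-only rate of 0.85, fixed-order effects of +0.10 and −0.10 turn 0.174 into 0.888 and 0.009. If 18 subjects had one order and 19 the other, with equal and opposite effects, the figure is 0.151, close to 0.174.

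**5. Limits of these figures.** They are per outcome. Section 12.3 requires all three together, and joint success cannot be more likely than any single one. If ease and pain were independent at 0.90 each, passing both has probability 0.651² = 0.42, before image quality. For pain, only the much-more category counts as failure, so a 10-point shift means 10 more or fewer subjects per 100 choosing that category; mild extra soreness may still be answered as about the same.

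**The case against.** **It is an optimisation study** (Section 12.2.2). Feedback on steering, lighting and fogging helps redesign whatever the order, and the implementation phase has its own protocol or amendment. This stands, and limits the consequence. It does not remove the point, because the summary and Sections 4 and 12.1 go further and claim non-inferiority.

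**The fixed order serves as a screen.** With SOC first, anyone with a complication or intolerance is stopped before the investigational exam (Sections 5.2 and 5.3). This stands as a possible reason, though the documents do not state it as one. A reason for the order does not remove the confounding.

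**Some items are asked per scope.** Video quality, satisfactory completion and structures viewed are rated separately for each scope. This stands, and the point is confined to ease and pain. Those items still come from a fixed sequence.

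**Randomising is not a cheap repair.** This stands too. The technical-issues item in the Supplemental Materials treats the second scope as the prototype, and the follow-up prompts on ease and discomfort also attach to the second scope. The ease scale mixes absolute end labels (very hard, very easy) with comparative ones. If SOC were second and rated very easy, flipping the score would record the FNS as very hard, which nobody said.

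A reader might infer that the order favours the FNS, or that the sequence is wrong and must be randomised. The documents support neither: they give no direction for the effect, and the sequence is tied to the screen.

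**Conclusion.** The confounding is complete for ease of use and pain. It follows from the sequence and the form of the questions, with no numerical assumption. For those two outcomes the plan claims a property of the device that its data cannot show, and more subjects will not change that.

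The size is unknown. Near the 90% threshold, assumed shifts of 5 to 10 points move the per-outcome pass probability across roughly 0.07 to 0.97, enough to reverse the decision in either direction. These figures rest on the assumed shifts, independent subjects, and each outcome taken through both looks on its own. They are not forecasts for the phase as a whole.

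It would go too far to say that the study is uninformative or that the image-quality ratings fail for the same reason. The feedback remains useful for redesign, and image quality is scored per scope. What needs correcting is the stated conclusion.

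**What to change.** **Recommended: restrict the claim.** In the Protocol Summary (Précis and Objectives), Section 4 and Section 12.1, replace non-inferiority of the device, for ease and pain, with wording such as: acceptable when used directly after a completed, uncomplicated SOC exam. Qualify the success definition in Section 12.3 in the same way; it does not use the term non-inferiority, but it is the rule that puts the claim into effect. Report the fixed order as a limitation with the results. All these places need to change together, or the protocol will contradict itself. The cost is a narrower and less favourable claim; no procedure or data item changes.

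**Option for the sponsor and treating team to consider: vary the order.** Whether this is acceptable is theirs to judge. It would require:

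- reconciling the screen on SOC complications and intolerance in Sections 5.2 and 5.3;
- changing the sequence text in the Protocol Summary and Sections 4 and 7.1;
- rewording the survey items tied to the second scope, and the success definition in Section 12.3;
- asking ease and pain directly as FNS against SOC, rather than reversing the existing scales;
- recording which scope came first and reporting results by sequence.

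This costs considerably more than the wording change, but it is the route that would let the ease and pain data address the device itself.

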Objectives:	
Optimize the low cost FNS by comparing to SOC scopes at Duke University Medical Center
 
We will compare the use and reliability of the FNS scope to SOC scopes available at Duke University Medical Center. This will include image quality to see structures, lighting, and steering mechanism. Key objectives include ease of use, image quality, and perceived pain. The technical and subjective feedback will optimize the device to gain efficiencies and improve tolerability. Success is considered to be that the FNS is overall non-inferior to the current SOC scopes.
 
The expected outcome is to have an optimized FNS scope for production and widespread implementation and use

Population:	Up to 50 subjects 18 years or older who meet clinical criteria to undergo a SOC endoscopic exam
Phase or Stage:	N/A
Number of Sites:	1 site
Description of Intervention:	The FNS is used for assessment of the entire upper aerodigestive tract by Ear, Nose, and Throat (ENT) doctors or otolaryngologists and is part of SOC in the USA. This scope is inserted through the nasal passages into the pharynx, enabling a full view of all areas at risk for Head and Neck Cancer (HNC). Study participation ends once the post intervention survey is completed.
Study Duration:	3 months
Subject Participation Duration:	About 30 minutes
Estimated Time to Complete Enrollment:	2 months

Recruitment: Adult subjects that will undergo SOC endoscopy at the Head and Neck Surgery and Communication Sciences clinic at Duke will be approached by their treating physician if they would be interested in participating in this study. If they are interested, the study team will approach them to review the written consent form. Once signed, the SOC procedure will take place followed by the study scope procedure. The physician will complete their portion of the post procedure survey and assess for adverse effects. The subject will complete a single question on the survey focused on comparing the pain from both procedures.

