12.3 Final Analysis Plan

Statistical Analysis – Aim 1: Optimization Phase.

1. Outcome 1 (Primary): The primary outcome is ease of use comparison between the FNS to the SOC scope (score of 1 – 5, with 1 being very hard and 5 being very easy).
2. Outcome 2 (Secondary): Quality of the image (image quality score range 1-5, with 1 being poor and 5 being excellent).
3. Outcome 3 (Secondary): Perceived pain between the FNS to the SOC scope (pain score range of 1 – 3, with 1 being much more and 3 being much less).

Scenario 1:

Success of this first phase 1 (Aim 1) after evaluating 37 subjects is defined as - (1) at least 90% response of ease of use of second scope compared to first score to range from same to excellent (3 to 5); and (2) 90% responding to better video quality of second scope compared to first (score ranging from same to excellent (3 to 5); and (3) 90% responding to pain score of same or much less (2 or 3); In short, this phase is a success if 90% respond to same to excellent/much less on all 3 of the outcomes.

[figure not shown]
Scenario 2: If the rate is between 50 to < 90% for any three outcomes in a sample from 37, then the plan is to proceed recruiting more subjects until 50 are recruited. At 50 subjects, if in scenario 1 then phase 1 is a success and phase 1 is complete; if not, fine tune the prototype.

Scenario 3: If the rate is < 50% for any one of the 3 outcomes described above, then the plan is to proceed to fine tuning the prototype.

The primary outcome of ease of use of scope as reported by the physicians, will be examined between the two different scopes, at the simplest level, using paired Z-test if the scores (or transformed scores) are normally distributed or by using Wilcoxon test if the scores are non-normal.

The analysis for secondary outcomes of the change in the quality of the videos and pain will each be examined using paired Z-test, if the change (or transformed scores) is normally distributed or by Wilcoxon test if the change is non-normal. Assumptions of each of these tests will be examined. The significance of each of the outcomes will be examined at alpha = 0.05. The reliability of this instrument (using intra-class-correlation (ICC)) will be first assessed by using the data from the first 50 subjects. If ICC is < 0.9, we will include training component and necessary adjustment for the physicians.

See diagram below

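### The 90% success rule in 12.3 is not the non-inferiority threshold that Section 4, 12.1 and the Summary say it is

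*Combined protocol and SAP*

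**What the plan says.** Three places define success as non-inferiority:

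- Protocol Summary, Objectives: "Success is considered to be that the FNS is overall non-inferior to the current SOC scopes".
- Section 4: "the threshold for success will be noninferiority of the FNS compared to the SOC scope". The sentences before it set the goal as FNS results at least as good as those of the SOC scope, and say that no further prototype is then needed.
- Section 12.1: the hypothesis is that "a low cost FNS can be non-inferior to the SOC scope in terms of ease of use, image quality, and perceived pain".

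None of them gives a margin, and none appears elsewhere.

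The decision rule is in 12.3. Scenario 1, at 37 subjects, requires "at least 90% response of ease of use of second scope compared to first score to range from same to excellent (3 to 5"), then "90% responding to better video quality of second scope compared to first (score ranging from same to excellent (3 to 5"), and "90% responding to pain score of same or much less (2 or 3"), all three together. If rates lie from 50% to below 90%, recruitment continues to 50 subjects. If 90% is still missed, the prototype is fine-tuned. A rate below 50% on any outcome leads straight to fine-tuning.

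Two other parts of the plan matter here. Section 12.2 gives a different success range, a proportion between 0.76 and 0.96. Section 12.3 also plans paired Z or Wilcoxon tests at 0.05, but they play no part in the success decision.

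**The concern.** A non-inferiority threshold asks whether the new scope is worse than the old one by more than a stated amount. The Scenario 1 rule asks whether more than one answer in ten is worse. These are different questions.

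Ratings vary from exam to exam. Two equally good scopes will draw some harder and some easier answers that balance. The rule counts the easier answers as successes, but no more so than same, so they cannot make up for the harder ones.

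Two things are at stake. A result of 90% or more could be read as demonstrated non-inferiority, which the rule does not establish. And a prototype that meets the aim in Section 4 may still be sent for fine-tuning under 12.3, with a further cohort of up to 50 subjects.

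**Working it through.** **The plan's own figure.** Section 12.2 gives n = 37 for a two-sided 95% interval of width 0.2 at a proportion of 0.9, with limits 0.76 and 0.96. The Wilson score interval at 0.9 with n = 37 is 0.763 to 0.962, width 0.199, and 37 is the smallest n with width at most 0.2. The figure reproduces. It concerns the precision of a single proportion and contains no margin against the SOC scope.

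**The rule in counts (12.3).** 33/37 = 89.2% and 34/37 = 91.9%, so the first look needs at least 34 of 37, that is, at most 3 worse answers. The second look needs 45 of 50, at most 5 worse. I take it that recruitment continues to 50 when at least 19 of 37 are successes.

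**An exactly equal FNS, comparative items (ease of use, pain).** Let t be the share of same answers, with the rest split evenly between better and worse. Then

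P(same or better) = t + (1 − t)/2 = (1 + t)/2.

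Setting (1 + t)/2 = 0.90 gives t = 0.80. The expected success share reaches 90% only if at least 80% of answers are ties. The documents give no tie share, so t is an assumption and is varied below.

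With p = (1 + t)/2, X₁ ~ Bin(37, p) and X₂ ~ Bin(13, p):

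P(pass by 50) = P(X₁ ≥ 34) + Σ (x = 19 to 33) P(X₁ = x) · P(X₂ ≥ 45 − x).

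| Ties t | Worse / better | p | Pass at 37 | Pass by 50 | Both ease and pain by 50, if independent |
|---|---|---|---|---|---|
| 90% | 5% / 5% | 0.95 | 0.89 | 0.97 | 0.93 |
| 80% | 10% / 10% | 0.90 | 0.49 | 0.65 | 0.41 |
| 70% | 15% / 15% | 0.85 | 0.17 | 0.26 | 0.06 |
| 60% | 20% / 20% | 0.80 | 0.04 | 0.07 | 0.004 |

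An 80% chance of passing one outcome by 50 needs about 84% ties.

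**Ranking of prototypes.** Only the worse share enters p. This comparison needs no symmetry and no assumption about equal scopes.

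| Prototype | Net (better − worse) | p | Pass one outcome by 50 |
|---|---|---|---|
| A: 8% worse, 0% better | −8 points | 0.92 | 0.81 |
| B: 15% worse, 30% better | +15 points | 0.85 | 0.26 |

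The rule favours A, although on balance A is rated below the SOC scope and B above it.

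**Image quality.** The item asks for a separate rating of each scope, for the FNS "Rate the video quality of the second scope: (Poor) 1 2 3 4 5 (Excellent"), while the criterion in 12.3 is worded as a comparison. If 3 to 5 means the FNS's own score, the (1 + t)/2 argument does not apply, and the criterion does not compare the scopes at all.

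**Precision of a net difference.** With 15% worse and 15% better, the variance per answer is 0.15 + 0.15 − 0² = 0.30. At n = 37 the SE is √(0.30/37) = 0.090, and the 95% half-width is 1.96 × 0.090 = 0.176, about 18 points.

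**The case against.** Several stronger readings are tempting, and the documents do not support them.

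- *That better ratings earn no credit.* They do: 4 and 5 on ease of use, and 3 on pain, count as successes. The defect is that they count no more than same.
- *That an equal FNS will often fail.* This depends on the tie share, which is not given; the chance of passing one outcome runs from 0.97 to 0.07 over the range shown. High tie shares are plausible for pain, where the only alternatives to the middle answer are much more and much less. Symmetry is also an assumption, since the SOC scope always comes first.
- *That a cohort below 90% would be reported as inferior.* No section says so. A miss at 37 leads to extension to 50, and a miss there to fine-tuning. The planned paired tests let better and worse offset each other, so balance would be visible in the results.

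Two further objections stand in part. Section 12.2 states a competing rule, under which an equal FNS with 80% ties would fall within the range (29 to 35 of 37) with probability 0.89 on one outcome, against 0.49 under the 90% rule at 37. The failure rates above therefore apply to 12.3 only. And a cap of 10% on worse exams is a defensible strict goal for an iterative optimization study. That defends the rule as a goal; it does not make it a non-inferiority threshold.

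**Conclusion.** The label is wrong as written. The Summary, Section 4 and 12.1 define success as non-inferiority, while the rule in 12.3 limits the share of worse ratings and has no margin. Meeting 90% does not establish non-inferiority, and missing it does not refute it.

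That mismatch, and the reversed ranking of prototypes (0.81 against 0.26), hold whatever tie share an equal scope would produce. How often an equal FNS would fail does rest on the assumed tie share and on symmetric answers. The equality argument covers ease of use and pain, and does not clearly cover image quality.

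**What to change.** 1. In the Summary, Section 4 and 12.1, describe the 90% rule as a performance goal (at most 10% rated worse) and remove the statement that meeting it is non-inferiority.
2. Reconcile the rule with the 0.76 to 0.96 success range in 12.2, so that one success criterion remains.
3. In 12.3, report for each outcome percent better minus percent worse with a 95% CI. For image quality, classify each pair of ratings by FNS minus SOC.
4. Make a non-inferiority statement only if the lower limit of that interval lies above a negative margin that was justified and fixed before the data are seen.

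The cost is protocol wording, the choice of a margin, and one table from data already collected. No extra subjects are needed. There are two drawbacks. The interval is wide, about ±18 points at n = 37 with 15% worse and 15% better, so a tight margin may not be met. And relabelling alone does not change how often an equal scope is sent for fine-tuning; if that matters to the sponsor, the decision rule itself would have to change.
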